5.2. Treatment Assignment

All subjects will receive the CSF infusion during the DBS surgery. The DBS surgery will be performed on the targeted nucleus either bilaterally or unilaterally, as previously determined by a multidisciplinary team of neurology, neurosurgery, and neuropsychology. During unilateral DBS surgery, the targeted nucleus will be infused using CED. The nondominant side will be infused during a bilateral DBS procedure.

5.3. DBS Surgery and Treatment Administration

5.3.1. Pre-surgical evaluation

Patients will undergo standard pre-surgical evaluations in preparation for surgery at the same time as their baseline assessment. This will include preoperative visits with the neurosurgeon and anesthesia team at the Preanesthesia Evaluation and Testing Center (PETC). Patient history will be taken with regards to any recent changes in medical status and a review of current medications both prescription and over-the-counter will be obtained by a qualified sub-investigator. Patients taking aspirin, other non-steroidal anti-inflammatory medications and vitamin supplements that include vitamin E will have been counseled to stop taking these at least 7 days before surgery which is our standard clinical practice for DBS surgery. Routine labs, including complete blood count with platelets, blood chemistries, PT/PTT, pregnancy test for women of childbearing age and urinalysis will be obtained, as well as 12 lead electrocardiogram and plain film chest radiograph when indicated. Additional studies specific to certain medical conditions and/or to ensure patient safety may also be obtained. The results of this detailed assessment will be recorded in written form on case report forms and recorded in the patients electronic medical record. Subjects will be instructed to be NPO and hold their PD medications after midnight prior to the surgery.

Table 2: Treatment day procedures

DBS surgery	Presurgical admission	Clinical practice
	General anesthesia	
	Reference MRI for stereotactic planning	
	Surgery for frontal burr hole	
	Stereotactic insertion of guide cannula	
Infusion	Lumbar puncture for 10 ml CSF	Research
	Insertion of microcatheter to unilateral GPi or STN	
	CED infusion of autologous CSF (<0.5 ml)	
	MRI monitoring of infusion	
Completion DBS	Replacement of microcatheter with DBS electrode	Clinical practice
	Wound closure	
	Implantation of pulse generator	

5.3.2. Initial DBS surgery

Patients will present to the pre-surgical area having not eaten since midnight and off all PD medications. They will be checked in by the pre-surgical staff, which includes placement of an intravenous line, baseline vital signs, and medication reconciliation as standard of care. After meeting with the anesthetic and surgical teams, the patient will be taken back to the operating room for general anesthesia and intubation. A lumbar puncture will be performed to obtain up to 10 ml of autologous CSF. This will be passed through a sterile 0.1 micron filter and maintained sterile.

Patients will then undergo MRI-guided DBS surgery in the intraoperative MRI suite (IMRIS) according to standard practice. Clinically, we utilize frameless stereotaxy (*ClearPoint, MRI Interventions*) for the surgery. A 1.5T reference MPRAGE MRI is acquired and then fused with preoperative 3T MRI of the designated target. GPi is optimally visualized with inversion recovery sequence and STN is best imaged with a T2 sequence. (The choice of stereotactic target, either globus pallidum or subthalamus, is a predetermined clinical decision made by a multidisciplinary team of neurology, neurosurgery, and neuropsychology.) The stereotactic trajectory is planned on a neuronavigation workstation by direct MRI visualization of the target nucleus: GPi or STN.

The scalp is prepped and draped and local anesthetic is infiltrated into the frontal incision. The incision is opened and a pre-coronal, frontal burr hole is drilled corresponding to the designated entry point from the stereotactic coordinates. A closed-dura technique is utilized to minimize loss of CSF and brain shift. A scalp mounted stereotactic frame (*MRI Interventions*) is attached to the burr hole. The bore of the magnet is draped with sterile technique, and the patient is moved into the bore of the magnet for the stereotactic portion of the surgery that is MRI guided and monitored.

5.3.3. Infusion Procedure

Once the patient is positioned within the MRI, the dura is sharply punctured with a sharp, ceramic stylet, and the MR-compatible infusion catheter is inserted. A second MRI is obtained to confirm the catheter position.

The research infusion of autologous CSF is initiated at 5 microliters/minute. Serial MRI monitoring of the infusion is obtained with T2 weighted images at approximately 15 minute intervals until the target nucleus can be visualized or until a total of 500 microliters is administered. The research infusion could add up to an additional 100 minutes to the patient's DBS surgery. MR imaging of the research infusion and then clinical assessment of the DBS electrode placement will be conducted on a 1.5T Siemens Espre system with continuous monitoring of both SAR and B1+rms values.

A Medfusion 3500 syringe infusion pump with a 1.0 milliliter BD glass syringe will be used with extension tubing (*Medex Micro Bore*, Product Code 536020, Smiths Medical, Dublin, OH, USA). The infusion catheter will be the SmartFlow™ K123605 (*MRI Interventions*).

5.3.4. Completion of DBS procedure

The microcatheter is removed, and replaced with the DBS electrode. There is no intraoperative, macrostimulation testing of the DBS electrode as the patient is asleep and electrode position is based on MRI targeting. The electrode is anchored in place, and the wound is closed. For bilateral cases, the contralateral (dominant side) DBS electrode will be inserted as per standard practice without the research infusion protocol.

The second stage of the DBS procedure is then performed on the same day and under the same general anesthetic for placement of the implanted pulse generator. For this, the patient is repositioned in a supine fashion with their head slightly rotated away from the pulse generator site. The ipsilateral scalp, neck, and chest are prepped and draped. The cranial incision is reopened and a small counter incision is made behind the ear. A subcutaneous pocket is made at the clavicular level. The DBS lead extension is tunneled

subcutaneously between the head and chest, such that the appropriate connections can be made from the DBS electrode to the lead extension and then to the pulse generator. Intraoperative lead impedance test is performed to confirm the electrical integrity of the system. The wounds are then copiously irrigated with antibiotic saline and closed. The patient is taken to the recovery area following extubation. Medications are reinstated, and they are observed overnight on a neurosurgical ward for one or two nights. Postoperative MRI is obtained standard of care, and the DBS system is maintained off until programming in the clinic. At the University of Virginia, we routinely perform a postoperative MRI after DBS surgery to assess the final position of the electrode. The imaging is conducted within the conditional limits set forth by the FDA for DBS systems. The final DBS system implanted will be assessed with MRI in one of two scenarios:

DBS systems that are full-body eligible:

- Neurostimulator models 37612 Activa RC, 37603 Activa SC, 37601 Activa PC
- No pocket adaptor can be implanted with the DBS system.
- Fully-implanted leads (ie, leads that are internalized and capped)
- No open or short circuits

DBS systems that are head-only eligible:

- Neurostimulator models 37602 Activa SC, 7428 Kinetra, 7426 Soletra
- Any DBS system that is implanted with a pocket adaptor
- Partially-implanted leads (ie, leads that are externalized)
- No open or short circuits

5.3.5. DBS programming and outpatient follow-up

The following is the standard clinical protocol for DBS programming in the outpatient setting: The wound is assessed at seven to ten days and surgical clips are removed. The DBS pulse generator is turned on at one month. For this first programming session, all patients present without having taken their PD medications since midnight. Each of the four DBS contacts is tested by escalating the stimulation to either symptom response or the induction of stimulation-induced side effects. High frequency stimulation is used at either 130 or 180 Hz. The optimal electrode configuration is selected, and then the patient takes their routine oral PD medications. They are observed for an hour for potential side effects with stimulation plus medication. Standard neurologic measures and PD assessments are performed in the clinic during stimulation testing. These include testing for tremor, bradykinesia, and gait. The patient is observed for potential dyskinesia after taking their medications. Follow up programming visits are then scheduled for two and three months postoperatively. At this time, stimulation and medications will be titrated for an optimal symptoms response. A full UPDRS assessment in the on and off state will be obtained at six months.

The patient and their caregiver will be trained in the management of the DBS device. They may have some ability to adjust the DBS amplitude within the parameters set by the neurologist. They will be able to interrogate their system at any time, and can disable the device in the event of an emergency. They will be instructed about the issues of an implanted pacemaker device, and to be cautious of strong magnetic fields.

As part of this research protocol, adverse events will be recorded during this first programming visit and each subsequent visit.

5.4. Concomitant Medications/Treatments

Prohibited Medications

Patients taking aspirin, other non-steroidal anti-inflammatory medications and vitamin supplements that include vitamin E will have been counseled to stop taking these at least 7 days before surgery. These medicines are contraindicated for DBS surgery.

Concomitant Medications

All medications and other treatments taken by a subject beginning at the baseline visit and continuing throughout the subject's participation in the study will be recorded on the Concomitant Medication CRF. Thereafter, Concomitant Medications information will not be collected or recorded in the eCRFs. The information documented will include the medication name, indication, dosage, and the dates of start and discontinuation.

At each visit, the site will obtain a complete listing of all medications currently being taken by the subject. Any changes, additions or deletions in the administration of concomitant medications will be recorded on the Prior and Concomitant Medications CRF. This information will also be documented in the subjects electronic medical record. Subjects may receive medications to treat safety events and routine treatment for underlying medical conditions as deemed necessary by the Investigator.

5.5. Duration of Study Participation

Subjects who are enrolled will be followed for six months after their DBS surgery. The Screening and Baseline period is a maximum of 90 days before the surgery and CED infusion. The follow-up period is the first 6 months post-DBS implantation. Follow up clinic visits correspond with routine post DBS clinic follow up and does not include additional visits specific to this research.

5.6. Discontinuation/Withdrawal from Study

Subjects may withdraw or be discontinued from the study at any time for any of the following reasons:

- Disease progression
- Inter-current illness that prevents further treatment
- Unacceptable adverse event(s)
- Subject decides to withdraw from the study
- Subject does not comply with study procedures (i.e. missed follow-up visits)
- At the discretion of the investigator
- Death

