4. SUBJECT ELIGIBILITY

Patients with medically-refractory Parkinson's disease who are planned for MRI-guided DBS surgery under general anesthesia are candidates for this protocol. They will be invited to participate in this study if they decide to have DBS surgery in the intraoperative MRI suite under general anesthesia. Patients who decide to have awake DBS surgery with clinical and electrophysiologic testing will not be eligible. The consenting process will occur in the outpatient clinic setting, and patients will have the opportunity to review the consent document at home with their families. A total of eight patients will be enrolled.

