5.7. Subject Status Definitions

Enrolled: All subjects who sign an informed consent will be considered enrolled in the study. All subjects consented on the study will be assigned to the research study in EPIC.

Screen Failure: A subject who is withdrawn or discontinues from the study prior to receiving DBS is considered a screen fail. Screen failures are not considered a study accrual and will be replaced. Note: The IRB defines any individual that has signed an informed consent as an enrollment in this study and so screen failures should be reported to the IRB with enrollment numbers.

On-Study: A subject is considered on-study on the date when the study team has confirmed the subject has met all of the inclusion and none of the exclusion criteria, and the treating physician/surgeon or study PI has signed off on the confirmation.

On-Treatment: A subject is considered on-treatment on the date that the DBS surgery is initiated. A subject who is withdrawn or discontinues from the study after receiving DBS surgery is considered a discontinuation and will not be replaced.

On Follow-up: A subject is considered on follow-up on the date that the DBS surgery is completed.

Off-Study: A subject is considered off-study if they are removed from the study for any of the reasons listed in Section 4.6, or if they have completed all study assessments through follow-up (6 Month follow-up visit).

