7.4. Early Termination Visit

In the event that a subject does not want to continue in the study until the 6 Month Follow Up visit, every effort will be made to complete a visit where final AE determination will be made. Subjects may withdraw voluntarily from participation in the study at any time. The subject will continue to be monitored on an annual basis as part of routine clinical care.

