8.1. Safety

The PI will evaluate all AE's that occur throughout the study and provide his assessment of the study safety profile as well as his recommendations for the study continuation. All AEs will be communicated to the FDA as part of the annual reporting for this proposed IDE study.

All AEs will be reported and categorized by investigators as definitely, probably, possibly, unlikely, or unrelated to the CSF infusion, and/or Parkinson's disease progression. Standard Code of Federal Regulation definitions for Serious Adverse Events (SAEs) and Unanticipated Adverse Device Effects (UADEs) will be used in assessment of AEs.

Primary safety endpoint for this study is the adverse event profile generated during the CED procedure through Month 6.

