8.4. Statistical Considerations and Sample Size

This is an open-label feasibility study of 4 subjects to be recruited from a single center. In order to find 4 eligible subjects suitable for treatment, up to 20 subjects may be consented and screened. For this study, a statistical sample size analysis is not proposed. All those subjects that were consented and then found not meeting study requirements will be considered screen failures.

The Safety and Effectiveness assessment will be descriptive with no statistical endpoints. The results will be examined and analyzed and used as a basis for determining the nature of future studies.

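### After the one-time infusion a subject may be taken off study for an adverse event, illness, progression or investigator discretion, and nothing keeps that subject's scheduled Month 1 and Month 6 assessments

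*Combined protocol and SAP*

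**What the plan says.** Section 5.6 states: "Subjects may withdraw or be discontinued from the study at any time for any of the following reasons". The seven reasons include disease progression, an intercurrent illness worded as preventing more treatment, unacceptable AEs, and investigator discretion. The others are the subject's own decision, non-compliance and death.

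Section 5.7 gives the consequence: "A subject is considered off-study if they are removed from the study for any of the reasons listed in Section 4.6". There is no section 4.6; the list is in 5.6. A subject who leaves after surgery "is considered a discontinuation and will not be replaced".

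The early termination visit in section 7.4 opens with "In the event that a subject does not want to continue in the study until the 6 Month Follow Up visit". Its stated content is a final AE determination, followed by annual monitoring in routine care.

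Section 8.1 sets the target: "Primary safety endpoint for this study is the adverse event profile generated during the CED procedure through Month 6". Section 8.4 gives the size: "This is an open-label feasibility study of 4 subjects to be recruited from a single center". Section 4 differs: "A total of eight patients will be enrolled".

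**The concern.** All study treatment is given on one day. From then on, leaving the study spares the subject no further study treatment; it only ends observation. Several of the listed reasons are themselves outcomes, or close to outcomes, so the decision to stop observing can depend on how the subject is doing.

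This matters most for progression. Section 9.5 names worsening of the movement disorder as one way infusion damage could show itself, and sections 3.1 and 8.1 ask for each AE to be attributed to the infusion and/or to Parkinson's disease progression. A subject who worsens could be removed for progression before the scheduled examinations that would help separate the two. The investigator who has discretion to remove is also the only safety monitor named (section 9.4.2).

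At stake are the completeness of the AE profile through Month 6 and the Month 6 efficacy and neuropsychology data, in a study small enough for one subject to change the picture.

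**Working it through.** The plan gives no figure to reproduce: section 8.4 says "For this study, a statistical sample size analysis is not proposed". The check sets the sections side by side and then sizes the possible loss.

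**1. What remains to discontinue after surgery.** Sections 5.2 and 6 describe one infusion during the DBS procedure. No later study treatment exists, so after that day 5.6 can only act on follow-up.

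**2. What off-study means.** Section 5.7 gives a removed subject the same status as one who has completed every assessment through Month 6. I found no text in sections 5, 7, 8 or 9 that continues the scheduled assessments for a removed subject.

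**3. What is scheduled after surgery (section 7.1).**
- Month 1: neurological exam and AE assessment.
- Month 6: neurological exam, AE assessment, neuropsychology, UPDRS, PDQ-39 and review of PD medication.

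UPDRS, PDQ-39 and neuropsychology have no other scheduled post-surgery time point. Any removal before Month 6 can therefore lose all of that subject's post-treatment values. Section 8.3 counts the neuropsychological and neurological exams as safety measures.

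**4. What other sections preserve.**
- Section 9: known AEs are followed until they resolve or stabilise, including those still present when participation ends. Related serious AEs may be reported at any time.
- Section 7.4: an AE visit is sought, but its trigger is the subject's wish to stop. Removal by the investigator is not named, and no neurological exam or UPDRS is specified.
- Not preserved by either: new AEs after removal that are not judged related, and the Month 6 examinations.

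**5. When AE recording ends.** Section 9 first ends collection at the 6 Month visit, then says recording continues to an End of Treatment visit. The section 7.1 schedule contains no such visit, so the end point for a removed subject is unclear.

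**6. Size.** The number and timing of removals are assumptions; the documents give no expected rate.
- Share of Month 6 data lost with one removal before Month 6: 1/4 = 25%. With eight subjects: 1/8 = 12.5%.
- Planned follow-up: 4 × 6 = 24 person-months. Share lost = k × (6 − m)/24 for k subjects removed at month m.

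| Removed | just after surgery | month 1 | month 3 |
|---|---|---|---|
| 1 subject | 6/24 = 25% | 5/24 = 20.8% | 3/24 = 12.5% |
| 2 subjects | 12/24 = 50% | 10/24 = 41.7% | 6/24 = 25% |

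The table shows loss of scheduled observation, not loss of the event that led to removal, which section 9 still covers.

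**The case against.** The case on the other side is substantial, and much of it stands.

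- **Section 9 covers the event behind a removal.** A reader might infer that removal hides the course and outcome of the very events the study is meant to describe. The documents do not support that: known AEs are followed after participation ends, and related serious AEs stay reportable.
- **Removals are counted.** The number of discontinuations due to AEs is itself a safety measure (section 3.1), so a removal for an AE appears in the results.
- **Removal is permitted, not required, and not only for bad outcomes.** A reader might infer that follow-up is cut short in exactly those who do badly. Section 5.6 says only that subjects may be discontinued, and it also lists subject choice and non-compliance. Section 5.5 plans six months of follow-up for everyone enrolled.
- **The list has a use before surgery.** It applies at any time, including the screening period of up to 90 days, when an illness could prevent treatment.
- **Non-replacement is not a fault.** Replacing treated subjects who did badly would make selection worse.
- **Zero-event limits do not measure the impact.** It is tempting to compare the one-sided 95% upper limit for 0/4, 1 − 0.05^(1/4) = 52.7%, with that for 0/3, 1 − 0.05^(1/3) = 63.2%. But a subject removed for an AE has contributed an event, and nothing drops an infused subject from the denominator.
- **Efficacy is secondary and descriptive.** UPDRS is a secondary objective without hypothesis testing, and section 5.3.5 makes the six-month UPDRS part of routine care.

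None of this closes the gap. No text says that routine Month 6 results would be used for an off-study subject, or that new AEs not judged related would be recorded.

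**Conclusion.** The point holds in a limited form. Sections 5.6 and 5.7 allow outcome-related removal from the study after a one-time infusion, and nothing keeps the scheduled Month 1 and Month 6 assessments for that subject. Capture of new AEs not judged related, and the Month 6 neurological exam, neuropsychology and off-medication UPDRS, can be lost selectively.

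One such subject is 25% of the Month 6 data at N = 4, or 12.5% at N = 8. This assumes that at least one infused subject is removed before Month 6 and that off-study status ends scheduled data collection, which is the natural reading of section 5.7 but is not spelled out. No test or power statement is affected, because the analysis is descriptive.

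**What to change.** 1. In 5.6 and 5.7, state that once the investigational procedure has begun (lumbar puncture), an AE, illness, progression or investigator decision does not end study follow-up. AE collection and the scheduled Month 1 and Month 6 assessments continue unless the subject withdraws consent, is lost to follow-up or dies. Lumbar puncture is the natural starting point because section 9 begins AE collection there and section 9.5 allows the infusion to be aborted after it.
2. Extend the 7.4 visit to every early exit, whoever initiates it, and include the neurological exam and UPDRS where feasible.
3. Correct the section 4.6 reference in 5.7, and reconcile the End of Treatment visit with the 6 Month visit as the end of AE recording.
4. Report follow-up time and reason for exit for each subject.

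This concerns data collection only and leaves clinical care to the investigator. The cost is a protocol wording change and one line per subject in the report. Section 5.5 says follow-up uses routine DBS visits with none added for research; the wider 7.4 visit may add an examination for a subject who exits early.
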